#### **Precessation Phase (TQD -2 weeks to TQD)**

There will be three phone contacts during the Precessation Phase.

*Precessation Call 1 (TQD -2 weeks).* Participants will engage in mobile assessments daily for 2 weeks during the Precessation Phase (EMA starting TQD-14d) while smoking ad libitum and prior to any pharmacotherapy treatment. The Precessation Call 1 will occur approximately 2 days after the start of EMA (TQD-12 days) to address any EMA problems (e.g., adherence or technical troubleshooting). Participants will complete a brief self-report assessment battery during this call.

*Precessation Call 2 (TQD -1 week).* Participants will receive smoking cessation counseling and complete self-report assessments at this phone call. This call will also involve dealing with any smartphone data assessment issues that arise during the Precessation Phase and instruction to continue mobile assessment for the next 1 week until the TQD.

*Precessation Call 3 (TQD -1 to -3 days).* This call will focus on preparing the participants for the TQD, reminding them of its date, and stressing the importance of complete abstinence after the TQD. Participants will complete the self-report assessments. This call will also address any EMA problems (e.g., adherence or technical troubleshooting).

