#### **Cessation Phase (TQD to +10 weeks)**

Participants will attend 2 study visits and 3 study calls during this phase.

*Cessation Call 4 (TQD Day +1-2).* Participants will receive smoking cessation counseling, complete self-report assessments including any smoking since their TQD. Participants will be reminded to attempt to completely abstain from smoking and use of all nicotine products. Mobile assessment data will be reviewed and problems with collection of such data will be addressed.

*Cessation Visit 2 (TQD Day +7).* Participants will receive smoking cessation counseling, complete self-report assessments including any smoking since their last visit, and provide breath CO and urine nicotine/cotinine samples. Participants will be reminded to attempt to completely abstain from smoking and all nonmedicinal nicotine products. Participants will be provided with an 8-week supply of C-NRT including nicotine patches and nicotine mini-lozenges with instructions on how to use them (through TQD +9 weeks). Participants will be encouraged to start the medication the following day and to use their medication adherently. Mobile assessment data will be reviewed and problems with collection of such data will be addressed. If a participant is unable to attend Visit 2 or Visit 3 (2 weeks post-quit; described below) we will conduct the appointment over the phone. Most study activities can be conducted remotely (self-report assessments, quit smoking counseling, medication education) with the exception of medication dispensation and physical tests (breath/urine smoking bioverification and blood pressure). In these cases, we will mail participants their study medication so they can still receive their nicotine replacement medication as soon as possible rather than delaying their medication dispensation until they are able to attend an in-person visit.

*Cessation Visit 3 (TQD Day +14).* Participants will receive smoking cessation counseling and complete self-report assessments including any smoking since their last visit, and provide breath CO and urine nicotine/cotinine samples. Participants will be reminded to attempt to completely abstain from smoking and use of all nonmedicinal nicotine products. Participants will be encouraged to use their medication adherently and any medication problems such as side effects will be addressed. Participants will be reminded of the follow-up phone contact planned for 9 weeks post-TQD and the incentives for taking the call.

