## Data Analysis Plan

### WSWS2 & MTWS-R Scoring:

The WSWS2-L (Smith et al., 2021) is a 19-item scale scored via one total score (mean) and 6 subscale scores (means). The WSWS2-B is a 6-item scale scored as one total score (mean). The WSWS2-L was assessed at all study phone calls and in-person visits (see Table 1-2 for assessment timeline). The brief version (WSWS2-B) was assessed at all EMA reports (3-6x/day), with the exception of TQD -1d through TQD +3d, while the long version (WSWS2-L) was assessed at the evening report (the WSWS2-L comprises the WSWS2-B items). Also see *Exploratory Withdrawal Symptoms* section below.

The MTWS-R is a 17-item scale with one item per symptom domain and no subscales. We will score one total score (mean) of the first 8-items that are DSM-5 symptoms as our primary MTWS-R score. We will score an exploratory MTWS-R including all 17-items (mean) that includes 'other possible symptoms' of smoking withdrawal. The MTWS-R and related information was derived from John Hughes UVM website describing the scale:

<http://www.med.uvm.edu/behaviorandhealth/research/minnesota-tobacco-withdrawal-scale>

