### Sensitivity to Abstinence:

The WSWS2 (-L and -B) should demonstrate a sensitivity to abstinence from smoking. We will examine whether WSWS2 total and subscale scores display significant increases from pre-quit to post-quit using a series of linear models. First, using EMA data (evening report) we will use piecewise models that allow for discontinuity (pre- vs post-quit day) to examine within-person changes in WSWS2 (-L and/or -B) from pre- to post-quit. We will examine differences in mean withdrawal severity during the week before vs after the quit-day, modeling the TQD jump (e.g., from 1w pre-quit mean to TQD) and post-TQD trajectory (e.g., slope, quadratic) over the first 3 days (WSWS2-L and WSWS2-B) and first week (WSWS2-B). Using study call/visit data we will examine within-person changes in WSWS2-L from an averaged baseline (averaged across pre-TQD calls/visits) to TQD +1-2d (Call 4) and TQD +1w (Visit 2). For EMA and Call data, we will examine the stability of baseline scores with and without approximately 1-3 days pre-quit to determine if there are anticipatory increases in withdrawal shortly before the TQD (and therefore exclude that rise from mean baseline calculations). We will examine sensitivity of WSWS2 to detect effects of smoking abstinence on withdrawal severity among the entire study sample as well as only among participants who self-report smoking no more than 2 cigarettes in the past 24 hours during the post-TQD timepoints as these individuals should still be experiencing significant withdrawal. We will examine several cigarettes/day cutoffs in sensitivity analyses to determine the robustness of results as function of this exclusion criterion (see below for *Sensitivity Analyses*). We hypothesize that both the WSWS2-L and the WSWS2-B will increase

significantly during the first 3 days and first week post-quit relative to pre-quit baseline values. Further, we expect increases to vary across the WSWS2-L subscales; we expect to see especially large increases in WSWS2-L subscales assessing craving, hunger, and concentration difficulties.

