In order to understand how short periods of abstinence might affect baseline (pre-cessation) scores and the pre-to-post jump in withdrawal, additional analyses will be undertaken to select pre-withdrawal scores that have occurred within 15 or within 30 minutes of smoking a cigarette during the baseline period. These will be used to generate pre-withdrawal or baseline estimates and then used in piecewise models to determine the pre-to-post cessation changes in withdrawal scale and subscale scores. This may constitute a more sensitive test of abstinence related withdrawal than will use of unselected baseline scores (e.g., all evening reports). Also, the relations of time-since-smoking data collected in the baseline period will be used as time varying covariates to study the relations of this with withdrawal severity in the same baseline reporting episode.

*Internal Consistency, Temporal Stability, Item Analysis, & Factor Structure:*

WSWS2-L total scale and subscale internal consistency will be assessed with Omega (McDonald, 1999) with bootstrap-corrected 95% confidence intervals (CIs). For comparison, we will also compute Cronbach's alpha coefficient (Cronbach, 1951). Ideally, both omega and alpha will be  $> 0.7$  for total scale and subscale at all timepoints. Further, we will examine response distributions and item-to-total correlations and subscale to total correlations. We will conduct parallel analyses for the WSWS2-B total scale (but with no subscale analyses).

We will examine internal consistency pre-TQD and at multiple timepoints post-TQD. We will examine internal consistency at Visit 1, which provides the largest sample size of participants pre-quit. We will examine internal consistency on the TQD (i.e., EMA evening report), TQD +1 to 2d (i.e., Call 4), and TQD +1w (i.e., Visit 2). This will provide estimates and comparison of the internal consistency at critical time points and assessment modalities (e.g., EMA mobile phone self-report, phone call with study staff, in-person tablet self-report) within the first week of the quit attempt.

We will examine the idiographic variability or lability of scales and subscales across the pre-TQD period. This will be compared with such variability in the post-quit period. Regression analyses will also be used to determine associations and shared variance during the pre-cessation period between Visit 1 (TQD  $>-2w$ ) and Call 1 (TQD -12d) and between Call 1 to Call 2 (TQD -7d).

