We will examine convergent validity using Pearson correlations between two assessment instruments, the WSWS2 and MTWS-R, which are both designed to measure the same construct: tobacco withdrawal severity. We will examine correlations between these two assessments on the same days during the pre-cessation phase (Visit 1, TQD >-2w) and cessation phase at TQD +1d to 2d (Call 4) and TQD +1w (Visit 2) when both are delivered at the same times and via the same delivery route. We will examine how both the WSWS2-L and WSWS2-B relate to the MTWS-R (8 and 17 item versions). Strong positive correlations will be supportive of convergent validity.

We will also examine convergent validity using Pearson correlations between the WSWS2 assessed at study Visits/Calls (Long form) and WSWS2 assessed via EMA (Brief form) for the corresponding time window. We will examine correlations between these two assessments on the same days during the pre-cessation phase (Call 1 and Call 2) and cessation phase (Call 4 and Visit 2). Strong positive correlations will be supportive of convergent validity across measurement modalities.

We will also examine whether specific WSWS2-L subscales (e.g., craving, negative affect) and exploratory subscales (e.g., anhedonia) positively correlate with other assessments that are administered at similar times: e.g., QSU total score, QSU factor 1, SHAPS anhedonia, WISDM craving subscale, that are designed to measure related constructs. We will examine Pearson correlations between WSWS2 subscales (e.g., craving, negative affect) and these other measures designed to assess the same/similar constructs at baseline (Visit 1), TQD +1 to 2d (i.e., Call 4), and TQD +1w (i.e., Visit 2). Likewise, we will examine whether these assessments that are designed to measure related constructs positively correlate with WSWS2 (WSWS2-L subscales or WSWS2-B items) assessed via EMA for the same corresponding time period. Positive correlations will be supportive of convergent validity for select subscale.

The WSWS2 should demonstrate meaningful positive relations with measure of tobacco dependence (e.g., WISDM-PDM, WISDM-SDM, FTCD, time to first cigarette) and possibly smoking heaviness (e.g., cigarettes per day, baseline exhaled CO). We will examine Pearson correlations between WSWS2 (WSWS2-L and WSWS2-B) on the TQD (via EMA) and baseline measures of tobacco dependence (Visit 1).

We will conduct similar measures of convergent validity with the MTWS-R versions.

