We will examine sensitivity to pharmacotherapy (nicotine patch + mini lozenge), which is hypothesized to decrease withdrawal severity. We will calculate residualized change scores (adjusting for pre-quit baseline) to quantify the change in WSWS2 total scale and subscale scores after 1 week of pharmacotherapy (Visit 3 scores, TQD +2w) relative to immediately prior to initiating pharmacotherapy (Visit 2 scores, TQD +1w) and separately, relative to a stable pre-quit baseline (Mean scores: Visit 1, Call 1, Call 2). We will examine these residualized change scores using GLMs to test whether the change significantly differs from zero and the corresponding effect size. We will examine unadjusted models as well as models controlling for medication dose (e.g., patch 7mg vs 14mg) and medication adherence. A valid assessment of withdrawal severity should be sensitive to decreases in symptoms following pharmacotherapy use.

We will conduct similar analyses with regard to the MTWS-R forms.

*Withdrawal Scale Comparison:*

As noted above, we will conduct parallel psychometric and validation analyses for the WSWS2-L, WSWS2-B, and MTWS-R, except when not possible due to constraints placed on single item-subscales (e.g., subscale internal consistency, CFA).

*Idiographic Examination of Withdrawal Waveforms & Prediction of Withdrawal Severity:*

We will examine plots of individual waveforms of withdrawal scores for the WSWS2 forms and subscales and the MTWS-R in order to reveal individual variation in withdrawal profiles over the pre-TQD and post-TQD assessment periods (e.g., peak, trajectory, average, variability, duration). Related to this, changes in symptom volatility and associations with episodic events (e.g., stressor occurrence, cue exposure) will also be examined in the pre- and post-TQD periods using piecewise linear models. The intent is to determine sensitivity to such events and to determine whether such sensitivity changes from pre- to post-TQD. Additionally, we will examine baseline factors (e.g., demographics, alcohol/cannabis use, chronic pain, anhedonia, anxiety/depression/stress, distress tolerance) that are most strongly associated with withdrawal severity during the pre-TQD and post-TQD periods.

*Craving Construct Exploration:*

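### The call/visit test of the WSWS2-L rise sets one mixed-mode baseline (one tablet score, three phone scores) against a phone score and a tablet score; a mode-matched check is a cheap improvement.

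*SAP*

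**What the plan says.** SAP, Sensitivity to Abstinence: after the EMA models, the call/visit analysis takes "within-person changes in WSWS2-L from an averaged baseline (averaged across pre-TQD calls/visits) to TQD +1-2d (Call 4) and TQD +1w (Visit 2"). One baseline serves both follow-up points. The same section allows the scores from the last 1-3 days before the quit day to be left out if they show an anticipatory rise; that would remove Call 3.

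SAP, WSWS2 & MTWS-R Scoring: "The WSWS2-L was assessed at all study phone calls and in-person visits". The protocol states "There will be three phone contacts during the Precessation Phase", and Table 1 of both documents schedules the WSWS2-L at Visit 1 and at each of those three calls. The protocol's Self-Report Measures section has the orientation battery completed on a computer or tablet.

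The SAP itself treats these routes as different. Its internal-consistency section compares "assessment modalities (e.g., EMA mobile phone self-report, phone call with study staff, in-person tablet self-report"), and its convergent-validity section compares the WSWS2 and MTWS-R at points where both are "delivered at the same times and via the same delivery route". No mode term or mode-matched baseline is planned for the change scores.

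SAP, Sensitivity to Pharmacotherapy: Visit 3 is compared with Visit 2 and, separately, "relative to a stable pre-quit baseline (Mean scores: Visit 1, Call 1, Call 2").

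Protocol, Cessation Phase: if a participant cannot attend Visit 2 or Visit 3, "we will conduct the appointment over the phone".

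**The concern.** A person may answer symptom questions differently when speaking to study staff than when filling in a screen. If so, part of a change between a mostly-phone baseline and a tablet follow-up reflects the route of administration, not abstinence. The error has opposite signs at Call 4 and Visit 2, because the one baseline lies between the two modes.

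What is at stake is narrow. The SAP hypothesises a rise over the first three days and the first week for both forms. Evening EMA carries the WSWS2-L only from TQD -1 to TQD +3, so the one-week rise in the WSWS2-L total and its subscales rests on Visit 2, the more exposed contrast. The MTWS-R is scheduled at calls and visits and is not listed in the EMA battery, so a parallel pre-to-post test of it would use the same mixed-mode data.

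The planned checks would not reveal the problem. The same-day comparisons of call/visit scores with EMA are Pearson correlations, which do not respond to a shift in mean. The Sensitivity Analyses section varies smoking status, not mode.

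**Working it through.** The documents give no effect size, SD or power figure for this contrast, so there is no stated figure to reproduce. The check is of how mode is weighted.

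**Inputs**
- Pre-quit WSWS2-L scores: Visit 1 and Calls 1, 2, 3 (Table 1, both documents).
- Modes: Visit 1 on computer or tablet (protocol, Self-Report Measures); Calls 1-3 by phone (protocol, Precessation Phase); Call 4 by staff phone call and Visit 2 by in-person tablet (SAP, internal-consistency section). Computer and tablet are treated as one mode, and Visit 3 in person as the same mode as Visit 2.
- m = mean tablet score minus mean phone score at equal true severity. It is not in the documents. Assumed size 0.1 to 0.3 SD; the sign is also unknown.

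**Step 1: error in a difference of means**

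Error = (tablet share at follow-up - tablet share in baseline) x m, for participants with complete scores.

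| Contrast | Baseline tablet share | Follow-up tablet share | Error | At m = 0.1 to 0.3 SD |
|---|---|---|---|---|
| Call 4, four-score baseline | 1/4 | 0 | -m/4 | -0.03 to -0.08 |
| Visit 2, four-score baseline | 1/4 | 1 | +3m/4 | +0.08 to +0.23 |
| Call 4, Call 3 dropped | 1/3 | 0 | -m/3 | -0.03 to -0.10 |
| Visit 2, Call 3 dropped | 1/3 | 1 | +2m/3 | +0.07 to +0.20 |
| Visit 3, baseline of Visit 1, Calls 1-2 | 1/3 | 1 | +2m/3 | +0.07 to +0.20 |
| Visit 3 against Visit 2, both in person | 1 | 1 | 0 | 0 |

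A negative m reverses every sign.

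**Step 2: visits held by phone**

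If a share f of Visit 2 is done by phone, the weight with the four-score baseline is (1 - f) - 1/4. The documents do not give f. At an assumed f = 0.10 it is 0.65; at f = 0.30 it is 0.45. The figures for Visits 2 and 3 in the table are therefore upper limits.

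**Step 3: precision cost of matching**

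With equal variances s² and equal correlations r, the variance of (follow-up minus the mean of k baseline scores) is s²(1 - r)(1 + 1/k).
- k = 4 (planned): factor 1.25.
- k = 3 (calls only, for Call 4): factor 1.33. SE ratio = √(1.33/1.25) = 1.03.
- k = 1 (Visit 1 only, for Visit 2): factor 2. Variance ratio = 2/1.25 = 1.60; SE ratio = √1.60 = 1.26. This is like cutting 232 participants to 232/1.60 = 145.
- Visit 3 against Visit 1 in place of the three-score baseline: 2/1.33 = 1.50; SE ratio = √1.50 = 1.22.

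**The case against.** The strongest defence is that the SAP puts single-mode evidence first. The EMA piecewise models cover the quit-day jump and the following course over three days for both forms, and over the first week for the WSWS2-B. That stands, and it confines the point to the call/visit contrasts.

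A second defence is that averaging four scores is a reasonable choice. Visit 1 is the only pre-quit tablet score, and it is also the first and earliest assessment, more than 14 days before the quit day. A contrast against Visit 1 alone, or a phone/tablet indicator, therefore separates mode from first-assessment effects only by assuming a stable baseline, or by leaning on participants who missed in-person visits, who are unlikely to be a random group. This also stands. It is why matching should supplement the averaged baseline at Visit 2, not replace it.

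Third, m may be negligible. Nothing in the documents excludes that, and nothing shows it.

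A reader might infer more than the documents support:
- *That the apparent course from Call 4 to Visit 2 carries the whole of m.* The arithmetic is right if someone takes that difference, but the SAP plans no such contrast; it models post-quit trajectory in the EMA data.
- *That the reliability comparison is invalid because time point and modality coincide.* The SAP offers estimates and a comparison across both and does not claim to separate them. It also includes Visit 1, which gives an in-person comparison with Visit 2.
- *That the pharmacotherapy test as a whole is compromised.* Its first-named comparison, Visit 3 with Visit 2, is matched when both are in person. A constant mode shift in the baseline used for adjustment does not move that mean change.
- *That the SAP overlooks modality.* It plans same-day cross-modality comparisons; they are only of a kind that misses a mean shift.

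**Conclusion.** The point holds in a limited form and is a cheap improvement, not a flaw in Aim 1 as a whole. The weights follow from the schedule: -m/4 at Call 4, up to +3m/4 at Visit 2 (-m/3 and +2m/3 without Call 3), and up to +2m/3 for Visit 3 against its pre-quit baseline. The SD figures rest wholly on the assumed range for m. The weights assume complete scores, in-person completion of Visits 2 and 3, and a mode effect that is the same before and after quitting.

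The Call 4 error is small. The main exposure is the size of the one-week rise in the WSWS2-L total and subscales, especially subscales that respond weakly, and any parallel MTWS-R test. The EMA findings stand apart from it.

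**What to change.** 1. **Call 4:** use the mean of the pre-quit calls as the baseline. This removes the mode difference for about a 3% larger SE.
2. **Visit 2, and Visit 3 against baseline:** keep the planned averaged-baseline contrast and report beside it either a contrast against Visit 1 or a mixed model of all call/visit scores with a phone/tablet indicator. Code visits held by phone as phone. Do the same for any MTWS-R test on these data.
3. **Same-day call/visit and EMA comparisons (Calls 1, 2, 4 and Visit 2):** add mean differences on the shared WSWS2-B items to the planned correlations. With EMA as the common reference, the Visit 2-minus-EMA difference less the call-minus-EMA difference gives some evidence on m.
4. **Interpretation:** draw the one-week WSWS2-L conclusion only where the averaged-baseline and mode-matched or mode-adjusted versions agree.

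The cost is SAP wording, one coded variable and a few extra results; the scheduled assessments already supply the scores. The Visit 1-matched contrast has about a 26% larger SE at Visit 2 (about 22% at Visit 3) under equal variances and correlations, and it relies on a stable baseline. Disagreement between versions may therefore reflect imprecision or a first-assessment effect as well as mode, and should be reported in those terms.

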## Significance

The Wisconsin Smoking Withdrawal Scale (WSWS) was developed over two decades ago to provide researchers and clinicians with a psychometrically sound, validated self-report assessment of nicotine withdrawal (Welsch et al., 1999). This 28-item scale includes a total symptom scale and 7 subscales addressing components of the tobacco withdrawal syndrome (e.g., anxiety, anger, sadness, craving, concentration difficulties, hunger, and sleep problems). The original scale has good psychometric properties, is sensitive to smoking abstinence, related to tobacco dependence measures, and has moderate predictive validity regarding smoking cessation outcomes. The WSWS has been a valuable assessment instrument that has been used by numerous researchers worldwide for investigating the nature and correlates of tobacco withdrawal. However, the field's understanding of tobacco withdrawal has advanced in recent years and the population of people who smoke has changed substantially (e.g., reduced smoking heaviness; Jamal et al., 2018; increased psychiatric comorbidity, Weinberger, Funk, Goodwin, 2016; Prochaska, Das, Young-Wolff, 2017). In addition, new components of withdrawal have been proposed (e.g., anhedonia; Cook et al., 2015; Hughes, Klemperer, Peasley-Miklus, 2020). Moreover, we believed that it was important to validate a short-form of this instrument in a contemporary sample of adults who smoke, one that would be suitable for situations where a long form would be impractical (e.g., population based studies, clinical use). These considerations motivated this effort to update and improve the assessment of withdrawal and validate a short-form scale.

We have recently developed a psychometrically robust, revised version of the WSWS (Smith et al., 2021), based on several recent smoking cessation trials conducted by UW-CTRI (Baker et al., 2016, Piper et al., 2018, Baker et al., 2021). This revised self-report assessment includes a long and brief version (Long: WSWS2-L; Brief: WSWS2-B) and comprises a revised stem, item wording, and response scale. The WSWS2-L is a 19-item scale that includes a total symptom scale and 6 revised subscales (i.e., negative affect, craving, concentration difficulties, hunger, restlessness, and sleep problems). The WSWS2-B is a 6-item scale that includes one item per symptom domain and may be useful in clinical or research contexts in which time or assessment burden is of high importance.

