## Study Overview

Adults who smoked cigarettes daily and desired to quit smoking enrolled in this study (N=232). This treatment-delay, one-group clinical trial was intended to validate and/or enhance the assessment of tobacco withdrawal amongst participants who try to quit smoking without using

medication early in the course of their quit attempt. Participants attempted to quit smoking and were instructed not to use any smoking cessation pharmacotherapy during the first week of their quit attempt. They initiated pharmacotherapy 1 week past the target quit day (TQD) and continued pharmacotherapy through 9 weeks past the TQD. This will allow for the examination of withdrawal symptoms for 1-week post-TQD in participants who are not using pharmacotherapy. Participants received 8 weeks of combination nicotine replacement therapy (C-NRT: nicotine patch + nicotine mini-lozenge) starting 1 week past the TQD. Participants received 4 counseling sessions (1 pre-TQD, 3 post-TQD) that conform to the US PHS Clinical Practice Guideline recommendations (Fiore et al., 2008). Participants completed 4 weeks of ecological momentary assessment (EMA) including a 2-week baseline (starting TQD -14d) and 2-week post-TQD (1-week un-medicated, 1-week using C-NRT). Enrolled participants completed an Orientation Phase, Pre-cessation Phase, Cessation Phase, and Follow-up Phase (Visit 4 only if self-reported 7d point prevalence abstinence). See Tables 1-3 below for timing of assessment and study activities.

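### The SAP expects craving, hunger and concentration difficulties to rise most after quitting, but plans no comparison between subscales, so this hypothesis cannot be confirmed or refuted

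*SAP*

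**What the plan says.** The SAP's Sensitivity to Abstinence section sets the analysis in one sentence: "We will examine whether WSWS2 total and subscale scores display significant increases from pre-quit to post-quit using a series of linear models". For the evening EMA reports these are "piecewise models that allow for discontinuity (pre- vs post-quit day) to examine within-person changes". For calls and visits, the within-person change in the WSWS2-L runs from an averaged pre-quit baseline to Call 4 (1-2 days after the target quit day, TQD) and to Visit 2 (one week after).

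The section closes with two hypotheses. The first is that the WSWS2-L and WSWS2-B rise after quitting. The second concerns differences: "we expect increases to vary across the WSWS2-L subscales", and "we expect to see especially large increases in WSWS2-L subscales assessing craving, hunger, and concentration difficulties".

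The WSWS2-L has six subscales (SAP, Significance), each scored as a mean (SAP, WSWS2 & MTWS-R Scoring). The three not named are negative affect, restlessness and sleep problems.

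**The concern.** A model of one subscale answers whether that subscale rises. It does not answer whether its rise exceeds another's. Two rises can differ although both are significant, and two rises need not differ although only one is. The second hypothesis is about the comparison, and the planned models do not make it.

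The question matters to the study. The SAP's Significance section gives the severity of different symptoms in people quitting without medication as a main reason for the work. Any statement about which symptoms respond most would rest on this analysis. The section also allows several time windows, two data sources, alternative baselines, and both the full sample and a low-smoking subset. Without a fixed comparison, nothing settles in advance which of these would count as support.

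**Working it through.** **Is a comparison planned elsewhere?** The plan gives no sample size, power or effect size for this hypothesis, so there is no figure to reproduce. I looked for a between-subscale comparison in the rest of the SAP and in the protocol's Analytic Plan, Exploratory Analyses and Power sections.

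- The baseline analysis restricted to reports within 15 or 30 minutes of smoking reruns the piecewise models for each scale and subscale, without comparing subscales.
- The comparisons that are planned answer other questions: pre- against post-quit variability, convergent against discriminant correlations, pre-quit scores against change scores as predictors of abstinence, and WSWS2 against MTWS-R.
- An effect size for a change score is named only under Sensitivity to Pharmacotherapy.
- The protocol sections contain no between-subscale test.
- No metric or threshold says what counts as an especially large rise.

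**What could the separate tests show?** Inputs: six subscales and N=232 enrolled (SAP). Assumed: two-sided 0.05, since the SAP gives no level for these tests; N=186, which is 80% of 232; rises d in SD units of the change score; correlation r between subscale changes. One change score per person is used, which simplifies the repeated EMA data. The power of one test is about Φ(d√N − 1.96).

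*Moderate rises, N=232.* At d=0.3: 0.3 × 15.23 = 4.57, and Φ(2.61) = 0.9955. At d=0.5 power is essentially 1.

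| True rises | All six significant (simulated, r = 0.3 and 0.6) |
|---|---|
| All equal, 0.3 | 97% |
| All equal, 0.5 | 100% |
| Named three 0.5, others 0.3 | 99% |

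The separate tests give the same result whether or not the rises differ. As a check on the third row with independent changes: 0.9955³ = 0.987.

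*A direct contrast in the same case.* Take the mean of the named three minus the mean of the other three. Its variance is 2(1 − r)/3, so its SD is 0.683 at r=0.3 and 0.516 at r=0.6. For a difference of 0.2, the expected z is 0.2 × 15.23 / 0.683 = 4.46, or 5.90 at r=0.6. Power is 99-100%, and simulation agrees. With smaller samples, simulated power is 95-100% at N=150 and 70-91% at N=75. When all six rises were equal, the contrast rejected in 4.0-5.6% of runs.

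*Small equal rises, N=186, d=0.20.* 0.20 × 13.64 = 2.73, so power p = Φ(0.77) = 0.779. The pattern that resembles support is all three named subscales significant and at least one other not. With independent changes its chance is p³(1 − p³) = 0.472 × 0.528 = 0.249. At r=0.6 simulation gives 12%. The range is therefore 12-25%.

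*A small subset.* The size of the subset smoking no more than 2 cigarettes in 24 hours is not given. At an assumed N=75 with equal rises of 0.30 and independent changes, p = Φ(2.60 − 1.96) = 0.738, and p³(1 − p³) = 0.402 × 0.598 = 0.24.

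**The case against.** The SAP nowhere says that a mix of significant and non-significant subscales will be taken as evidence of a difference. A reader might infer it from a criterion built on significance, but the hypothesis is worded in terms of size, and the piecewise models do estimate a size. That objection stands: misreading is a risk and not a stated rule.

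A reader might also take any mixed pattern as false support. At d=0.20 and N=186 some but not all of the six tests are significant in 48-78% of runs (r from 0.6 to 0). Most such patterns would not favour the three named subscales. The relevant figure is 12-25%, and exactly those three and no others are significant in only about 0.5% of runs: p³(1 − p)³ = 0.472 × 0.0108 = 0.005. With equal rises of 0.30 and N=232, any mix at all occurs in only about 2-3% of runs. Nothing in the documents says that rises will be small, and studying unmedicated quitters points the other way. This also stands, but larger rises do not repair the plan, because all six tests are then significant and uninformative about differences.

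Last, this is a follow-on expectation, and the section's main hypothesis is matched by its analysis. That limits the weight of the point. Judging size from the estimates is reasonable description, but without a metric, window or contrast it does not test a hypothesis written into a registered analysis plan.

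**Conclusion.** The point holds as a gap in specification. The SAP states a hypothesis about differences between subscales and plans only separate tests of whether each rises, so those tests cannot confirm or refute it. With moderate rises they are uninformative: all six are significant in about 99% of runs even when the rises truly differ (0.5 against 0.3, N=232). With small rises or small subsets they could mislead: 12-25% of runs at equal rises of 0.20 SD and N=186. The rises, the correlations, the 186 and the subset size are assumptions; only the 232 and the six subscales come from the documents. The documents do not support saying that the investigators will read mixed significance as a difference. It is a cheap improvement to a secondary hypothesis, and the section's main analysis is unaffected.

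**What to change.** Add one model and one contrast.

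- **Data.** Use the call and visit WSWS2-L scores, from the averaged pre-quit baseline the SAP already plans to Call 4, repeated at Visit 2. State beforehand how the SAP's check for anticipatory rise decides whether Call 3 enters that baseline. The EMA evening reports suit this less well, because the long form was given there only from TQD-1 to TQD+3, which leaves one pre-quit evening.
- **Sample.** Full sample as the main analysis, with the subset smoking no more than 2 cigarettes in 24 hours as a sensitivity analysis.
- **Model.** Fit all six subscales in one mixed model with a subscale-by-phase interaction. Test one contrast fixed in advance: mean rise of craving, hunger and concentration difficulties minus mean rise of negative affect, restlessness and sleep problems, with its 95% confidence interval.
- **Metric.** Report the contrast on the raw item-mean scale and on a scale divided by the pre-quit SD, with one named as primary beforehand.
- **Separate models.** Keep them for estimation.
- **Status.** At registration the SAP reports that only monitoring data had been reviewed. If outcome data have since been examined, label the contrast as added after registration.

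No new data are needed. The costs are that the result can depend on the metric, since dividing by the pre-quit SD may change the ranking of subscales, and that the three-against-three contrast is only one way to express an expectation for which the SAP sets no contrast.
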